## **6. Participant selection**

Two hundred twenty-five depressed, medically stable males and females between the ages of 18 and 65 will be recruited for this study. All subjects (50% males and 50% females) will meet criteria for current major depression (MD). An equal number of participants will have CRP values from each of the three risk groups, as defined by CDC/AHA guidelines: <1mg/L (low), 1-3 mg/L (moderate), and >3mg/L (high). Based on retention rates in previous studies by our group utilizing a similar design in depressed subjects, we anticipate that recruiting 225 subjects will provide analyzable data for approximately 80 subjects. There will be no exclusions for race/ethnicity and minority populations and women will be actively recruited to ensure that 50% of the subjects will be female. We will make active attempts to enroll minority patients in a proportion that is reflective of the greater Atlanta metropolitan area from which patients will be recruited. No patients will be enrolled from vulnerable populations, including neonates, children, prisoners, or institutionalized individuals. No use will be made of fetal tissue. Patients will be obtained from multiple referral resources including the Emory Clinic, Grady Health System, the Veterans Administration Medical Center (VAMC), and community psychiatrists. In addition, subjects will be obtained from ongoing clinical trials including the Mental Health Centers for Intervention Development and Applied Research (CIDAR) trial, which is scheduled to enroll 400 subjects over 5 years. Depressed subjects will also be obtained from newspaper and radio advertisements as well as internet solicitation. Subjects in this study may also be referred from our Behavioral Immunology Program "Recruitment Clinic" protocol, Clinical Research in Psychiatry: IRB0000075162, which uses the screening strategy similar to this protocol to recruit and screen patients with depression for our active studies through IRB approved social media campaigns. Subjects who are determined to be eligible for this study will be referred to study staff. Participants who have consented to any Emory Behavioral Immunology Program studies will be given an option to consent to have any screening and study data used in future studies, including this study. If the participant consents to this option, any previously completed screening or study assessments may be used

in the current study to help reduce patient burden. Some labs or evaluations may be repeated at the discretion of the PI or PI's designee, if more current data is needed. We anticipate that at least 2 subjects per month (~24 subjects per year) will consent to enter this study. This estimate is based on ongoing projects that have been recruiting subjects for related studies over the past 5 years. Of subjects who meet entry criteria, our past experience suggests that approximately 20% will discontinue study participation.

Patients with MD enrolled in the study will meet DSM-V-TR criteria for a current major depressive episode without psychosis with a symptom severity score of  $\geq 18$  on the Hamilton Depression Rating Scale (HDRS) -17 item scale. To be included, subjects must not demonstrate active suicidal intent or plan and must score  $\leq 2$  on the HDRS or QIDS suicide item, and must have no suicide attempt within six months of screening. Enrolled subjects will have no history of the following: schizophrenia, schizoaffective disorder, other (non-mood disorder) psychosis, depression secondary to a medical condition, mental retardation, and substance dependence [or abuse within the past year (except nicotine)], dementia or MMSE  $<28$ , unless otherwise approved by the PI or PI's designee, or delirium. Subjects will be at risk for exclusion for a urine toxicology screen positive for ETOH or drugs of abuse. The presence of post-traumatic stress disorder, panic disorder, obsessive compulsive disorder or social phobia will not disqualify subjects from enrollment as long as depression is the primary diagnosis, though post-traumatic stress disorder may be considered as a covariate in statistical analyses. Enrolled subjects may have a comorbid personality disorder; however, subjects who meet criteria in clinical interview for antisocial personality disorder will be disqualified, as will subjects with a history of hospitalization and/or recurrent suicidal behavior judged to be directly due to the personality disorder.

Potential subjects may be excluded for a number of medical conditions that might confound relationships between depression and inflammation, or contraindicate MRI scanning or administration of L-DOPA, including uncontrolled cardiovascular disease, autoimmune condition (i.e. rheumatoid arthritis, inflammatory bowel disease, multiple sclerosis, lupus), current or history of migraines or headaches with frequency  $>6$  headaches per month, glaucoma, melanoma, or bleeding disorder of any kind, embedded metallic objects, prosthetics made of paramagnetic metals, aneurysmal clips, a history of claustrophobia, chronic infection (i.e. HIV, hepatitis B or C, herpes), abnormal lab results deemed by study physicians as contraindicated for study participation, or pregnancy. Similarly, patients may be excluded for evidence of medical or neurological abnormality on physical examination. Subjects who develop signs of an infection between screening and commencing the protocol assessments will be rescheduled when symptoms have resolved, if agreeable to the subjects.

## 7. Statistical Analysis

**Power Analysis:** To ensure a range of inflammation from low to high, we will analyze an equal number of participants from low to high inflammation levels: approximately 27 patients with CRP  $<1$ mg/L, 27 patients with CRP 1-3mg/L, and 27 patients with CRP  $>3$ mg/L. We recently completed a study using a similar enrollment strategy and analyzed data from ~80 medication-free subjects over a similar time frame. Based on our preliminary data, we anticipate large effect sizes (Cohen's dz  $\sim 1$ ) for L-DOPA-induced increases in connectivity in patients with high inflammation; thus with n=30 per group we will have  $>80\%$  power at  $\alpha=0.05$ .

### Interim Monitoring and Early Stopping:

Subjects will receive a physical examination and laboratory testing for safety as well as tests for pregnancy (if female) and substance abuse at screening.

Subjects will be at risk for study discontinuation with the following events:

- Substance abuse
- Protocol violation

The following events are considered sufficient reasons for discontinuing a subject from the study:

- An adverse event (AE) that, in the judgment of the investigator or study physicians, may cause severe or permanent harm
- Subject withdraws consent
- Subject lost to follow-up
- Pregnancy

- Death

### **Analysis Plan and Statistical Methods:**

Descriptive statistics will be used to describe the central tendencies and variances of dependent variables and demographic and clinical characteristics of the patients. Due to the pilot nature of this project, we will use both targeted and exploratory data analysis methods to determine whether L-DOPA increases corticostriatal connectivity in depressed patient with high versus low inflammation. Statistical modeling will be conducted as described below. Log-transformation will be used for non-normally distributed data. Statistics will be two-tailed with alpha <0.05, and conducted in SAS and SPSS.

**Analytic Strategy, Objective 1:** The primary outcome will consist of a targeted, hypothesis-driven approach including extraction of individual patient level Z scores for connectivity with ventral or dorsal striatum and regions of interest identified in our previous work that 1) exhibited alterations in connectivity between patients with high and low inflammation, and 2) were significantly associated with behaviors of interest. Post-L-DOPA or placebo administration Z scores will be entered into linear models controlling for pre-administration connectivity scores as well as relevant covariates. The difference (delta; post minus pre) in connectivity Z scores before and after placebo and L-DOPA will also be compared by paired T test, and between patients with high and low inflammation (CRP > or < 3mg/L). Generalized linear mixed model (GLMM) will be used to assess whether corticostriatal connectivity is improved by L-DOPA, and whether effects depend on concentrations of CRP, while controlling for clinical and demographic covariates. Linear regression models will be used to determine whether increased CRP is associated with decreased response to hedonic reward, as assed at by fMRI using the MIDT. Response to hedonic reward (as measured by MIDT) will also be used to assist in interpretation of resting-state connectivity data before and after L-DOPA administration in two ways: 1) Striatal regions activated in response to reward will be used to corroborate location of the striatal seed regions for resting-state connectivity analysis, and 2) responses to the MIDT will be entered into GLMM models to determine whether decreased reward sensitivity predicts greater increase in connectivity after L-DOPA. White matter integrity as measured by DTI will also be used to assist in interpretation of responses to L-DOPA, as subjects with less cortical-striatal-thalamic anatomical connections may have less ability to respond to increases in dopamine. To identify other corticostriatal circuits that may be affected by increasing dopamine precursor, striatal seed-to-whole-brain comparisons of L-DOPA versus placebo, will be performed as a secondary analysis strategy. In the event that CRP fails as a classification or correlational variable, exploratory analyses will be conducted using other measures of inflammation described above for Objective 1.

**Analytic Strategy, Objective 2:** Similar to the analytic strategy for Objective 1, post-L-DOPA or placebo administration neurocognitive performance or self-report scores will be entered into linear models with CRP (or other inflammatory markers) while controlling for pre-administration behavioral scores as well as relevant covariates. The difference (delta; post minus pre) in behavioral scores before and after placebo and L-DOPA will also be compared by paired T test, and between patients with high and low inflammation (CRP > or < 3mg/L). L-DOPA-related changes in functional connectivity in Objective 1 will then be compared to relevant post-LDOPA task-based and self-report behavioral responses using linear modeling.

**Analytic Strategy, Objective 3:** Relationships between functional connectivity and behavior before and after L-DOPA with central and peripheral inflammatory cytokines and their soluble receptors, and biomarkers of their potential effects on dopamine through decrease BH4 activity will be explored. Gene transcripts associated with inflammatory and metabolic signaling pathways related to inflammation effects on the brain have been used to predict response to pharmacological therapies (54, 95), including our previous work (96, 97). Therefore, genome-wide gene expression will be assayed. Plasma and CSF will be collected on a separate visit to measure IL-6, IL-1 $\beta$ , TNF and their soluble receptors, CSF BH4, dopamine, HVA and DOPAC, and plasma phenylalanine and tyrosine. Linear regression will be used to examine relationships between functional connectivity Z-scores or behavior (dependent variables) and biomarkers of inflammation and dopamine synthesis (independent variables), while controlling for covariates. Cytokines and their receptors will be examined first independently (with and without correction for multiple comparisons), then together in models to identify biomarker(s) that are most significant after backward and forward linear regression. If variables are collinear (as assessed by variance inflation factor, tolerance and leverage plots), principal component analysis (PCA) will be used.(98) Gene expression that correlates with CRP, or differs between patients with

low versus moderate versus high CRP (<1, 1-3, and >3 mg/L) will be determined (5% FDR,  $p<0.05$ ). Gene lists will be analyzed for over representation of functional pathways and transcription factor binding regions per our previous work, (96, 97, 99) and correlated with connectivity Z-scores.

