### **Inflammation effects on corticostriatal connectivity**

Dopamine regulates reward, cognitive and motor activity via projections to ventral and dorsal striatum, as well as prefrontal cortical, limbic and other subcortical brain regions, all of which are highly interconnected. Whereas ventral striatum is thought to mediate motivation and reward, the more dorsal regions are thought to mediate motor and cognitive functions, yet substantial neuroanatomical and functional overlap exists to allowing for integrative processing of information and behavioral output (32, 33). To examine the extent to which inflammation-related decreases in dopamine affect functional connectivity between ventral and dorsal subdivisions of the striatum and other brain regions (15, 32), we conducted resting state fMRI in medically healthy, medication-free depressed patients with varying levels of inflammation as defined by plasma CRP (34). Interestingly, we observed significant negative relationships between inflammation and functional connectivity of the ventral and dorsal striatal with several other cortical, limbic and subcortical brain regions in a whole brain analysis (adjusted  $p < 0.01$ ), either using CRP as a linear variable or when stratifying patients by high versus moderate versus low inflammation (CRP  $> 3$  versus 1-3 versus  $< 1$  mg/L, respectively) (34). For example, patients with low inflammation exhibited significant positive connectivity between ventral striatum and the ventral medial prefrontal cortex, as well as other cortical, subcortical and limbic structures, consistent with previously published maps of functional connectivity between ventral striatum and other brain regions in healthy controls (1, 32, 35, 36). Conversely, little positive connectivity between ventral striatum and subcortical and limbic brain regions was observed in patients with high inflammation, and connectivity with ventral medial prefrontal cortex was completely absent in these patients, which differed significantly between groups after whole brain correction ( $p < 0.01$ , peak voxel in Brodmann area 32). The ventral medial prefrontal cortex is functionally connected with the striatum and thought to play a role in motivation, reward and anhedonia (21, 37, 38). Interestingly, Z scores representing the degree of correlation between left ventral striatum and ventral medial prefrontal cortex were associated with severity of depressive symptoms as measured by Inventory of Depressive Symptomatology-Self Report, which was significant after adjusting for age, sex and body mass

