
index. This relationship was mediated by scores for symptoms of anhedonia, indicating that patients with low or negative connectivity scores exhibited higher self-reported symptoms of anhedonia. This ventral medial prefrontal region is consistent with previously identified regions of interest (ROIs) in meta-analyses as activated by a wide variety of rewarding stimuli in healthy controls (39), and decreased connectivity between this region and striatum has been previously observed in anhedonic patients who did not respond to a novel antidepressant treatment (40).

Regarding inflammation-related differences in connectivity with dorsal striatum, patients with high and low inflammation exhibited similar positive connectivity between dorsal striatal subregions and motor cortex. However, loss of functional connectivity between the dorsal caudal putamen and frontal cortical regions were observed in patients with high inflammation. These findings indicate that even within dorsal striatum, inflammation-related changes in corticostriatal connectivity may be specific to frontal cortical, but not motor, brain regions. Decreased connectivity between dorsal caudal putamen and anterior prefrontal cortex (Brodmann area 10) were associated with scores on the Trail Making Test-A, an objective measure of psychomotor speed, demonstrating greater psychomotor retardation in patients with low connectivity ( $r=-0.59$ ,  $p<0.05$ ) that was significant when controlling for age, sex and BMI. Of note, decreased glucose metabolism has been observed in similar prefrontal cortical regions of IFN-alpha-treated and depressed patients that are thought to play a role in psychomotor slowing (26, 41). Together, these findings support the hypothesis that increased inflammation decreases corticostriatal functional connectivity, which may contribute to dopamine-related symptoms of anhedonia and psychomotor slowing. Therefore, corticostriatal connectivity may serve as a brain biomarker of inflammation effects on dopamine that can be used to assess the efficacy of therapeutic targets to reverse inflammation-related changes in neural circuitry and behavior (42).

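### The plan's only remedy for non-normal data, a log transformation, cannot be applied to connectivity Z scores or change scores, which can be zero or negative

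*Combined protocol and SAP*

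**What the plan says.** The general paragraph of section 7, Analysis Plan and Statistical Methods, states: "Log-transformation will be used for non-normally distributed data". It does not say which variables the rule covers, how normality is judged, or what happens where a log is impossible. Section 7 names no offset, rank method, robust method or resampling method as an alternative.

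Under Analytic Strategy, Objective 1, the primary outcome rests on "extraction of individual patient level Z scores for connectivity with ventral or dorsal striatum and regions of interest identified in our previous work". Post-dose scores enter linear models adjusted for pre-dose scores, and a generalized linear mixed model (GLMM) tests the L-DOPA effect and its dependence on CRP. In addition, "The difference (delta; post minus pre) in connectivity Z scores before and after placebo and L-DOPA will also be compared by paired T test". Objective 2 repeats the difference-score tests for behavioural measures.

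Section 3, Inflammation effects on corticostriatal connectivity, describes the earlier outcome as "Z scores representing the degree of correlation between left ventral striatum and ventral medial prefrontal cortex". It reports that "patients with low or negative connectivity scores exhibited higher self-reported symptoms of anhedonia", and says of the high-inflammation group that "connectivity with ventral medial prefrontal cortex was completely absent in these patients".

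**The concern.** A correlation-based score can fall below zero, and the background section says that it did. A post-minus-pre difference is negative whenever the value falls between scans. The rule therefore prescribes an operation that does not exist for part of the range of the main outcome and for every difference score.

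If one of these variables were judged non-normal, the analyst would have two ways to obey the sentence. Software that sets the log of a non-positive number to missing would remove observations according to their outcome. A constant added first would keep them, but the constant is not specified and the p-value depends on it. Either way, a choice affecting the main comparison would be made after the data are seen.

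**Working it through.** **The plan's own figure.** Section 7 states power above 80% with 30 per group, dz about 1 and two-sided alpha 0.05. The paired t test (noncentral t, df = n − 1) gives 99.96% at n = 30 and 99.88% at n = 27, the approximate group size in the same paragraph. The stated bound holds and is not in dispute.

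**Inputs not in the documents.** The mean and SD of the Z scores, the correlation between the two visits' differences, and the normality criterion are not given. All are assumed below.

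**Share of Z scores without a log.** For a normal variable this is Φ(−mean/SD):

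| Mean/SD | Share | Of 27 |
|---|---|---|
| 0 | 50% | 13.5 |
| 0.5 | 31% | 8.3 |
| 1 | 16% | 4.3 |
| 2 | 2% | 0.6 |

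The loss differs between groups. If the high-CRP mean is 0 and the low-CRP mean is 1 SD, the groups lose 50% and 16%. The true gap of 1.0 SD shrinks to 0.49 SD among the values kept.

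**Paired difference test, literal deletion, log always applied.** Assume n = 27, normal differences, placebo mean 0, equal SDs and correlation 0. The L-DOPA mean is then dz × √2 SDs.

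- At dz = 1, P(placebo > 0) = 0.50 and P(L-DOPA > 0) = Φ(1.414) = 0.921. Both are positive in 0.50 × 0.921 = 0.461 of pairs, and 27 × 0.461 = 12.4 pairs. Simulated power falls from 99.9% to about 55%.
- At dz = 0.5, 0.50 × Φ(0.707) = 0.50 × 0.760 = 0.380, and 27 × 0.380 = 10.3 pairs. Simulated power falls from 71% to about 13 to 14%.
- With correlation 0.5, power after the log is about 63 to 64% at dz = 1 and 18% at dz = 0.5.

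**The same test with the rule used only when triggered.** Assume the log is taken when Shapiro-Wilk rejects at 5% for either difference; the plan names no test.

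| Assumed data | Rule fires | Power, dz = 1 | Power, dz = 0.5 |
|---|---|---|---|
| Normal | about 10% | 99.9% to 95.6% | 71% to 64.7% |
| Heavy-tailed (t, 3 df) | about 66% | 99% to 91% | 77% to 48% |

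**An added constant.** Assume normal differences with SD 0.2, dz = 0.5, n = 27 and correlation 0. In each simulated trial, differences are shifted so that the smallest equals a constant. Power is 43%, 56%, 65% and 69% for constants 0.001, 0.01, 0.1 and 1. In 28% of trials, significance at 0.05 changes with the constant.

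**The case against.** The strongest reply is that the sentence was meant for measures where a log makes sense, such as plasma CRP and cytokines, and that no competent analyst would log a signed score. Nothing in the documents says that the Z scores or differences are non-normal, so the rule may never reach them. This stands as a limit on the harm. It does not repair the text, which names no variables and leaves the primary outcome without a usable procedure if normality fails.

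A reader might go further and infer that the plan discards patients, or that its primary analysis would have only 55% power. The documents support neither. The plan prescribes no deletion. The 55% and 14% figures log normal data, on which the rule should rarely fire, and they concern only the paired t test, which supplements the linear models and the GLMM. No power loss has been shown for those models.

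A reader might also infer that the lost observations are the low-connectivity patients of interest. That can apply to raw Z scores only. A negative difference means that connectivity fell between two scans, not that it was low, and most pairs lost in the simulation go because of placebo differences at or below zero.

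**Conclusion.** The fault is real and small. That the rule cannot be applied to signed variables is a matter of arithmetic and needs no assumption beyond the plan's own description of those variables.

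The size is doubly conditional: a normality check must fail, and the analyst must then take the log literally or choose a constant. On the assumed ranges, 2% to 50% of Z scores would have no log. For the supplementary paired test with literal deletion, the always-log power figures of about 55% (dz = 1) and 14% (dz = 0.5) are a worst case. With a trigger, the loss is about 4 to 6 points for normal data and 8 to 29 points for the heavy-tailed example. All of these rest on assumed means, SDs, correlations and a trigger test that the documents do not give. Correcting the rule would be good practice; the trial does not depend on it.

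**What to change.** Replace the sentence with wording such as:

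> Strictly positive skewed measures (CRP, cytokines, reaction and completion times) are log-transformed before any differencing. Connectivity Z scores and change scores are analysed untransformed. Normality is judged on model residuals or, for paired tests, on the within-patient differences, by a criterion stated in advance. If it fails, the paired comparison of changes uses a within-patient sign-flip permutation test, and the covariate-adjusted linear models and the GLMM use patient-level bootstrap intervals.

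One fallback is named per analysis for two reasons. A list of options would restore the post hoc choice, and the sign-flip test suits the paired contrast but does not carry over directly to the covariate-adjusted models or the CRP-by-treatment GLMM. Resampling whole patients keeps each patient's two visits together.

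The cost is a short change to the analysis plan and slightly more programming. No observation is lost to transformation, and neither the sample size nor data collection changes.

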**Gender and Minorities:** Based on the composition of the patients treated for major depression at the Emory Clinic, Grady Health System, VAMC and community psychiatry clinics, we anticipate that an equal number of men and women will be included in the study. As for the racial composition of the sample, we anticipate 30-40% African Americans, 5-10% Latinos and 2-5% Asians, which is reflective of the community (city of Atlanta) from which our sample will be drawn.

**Dropouts:** Because participation in this study involves two screening visits followed within approximately 2 weeks by three study visits, we anticipate that there will be few subjects who will drop out between screening and the study visits. In our experience, however, there will be subjects who will have to be removed from the study because of a positive urine toxicology screen. In addition, some subjects may become too severely depressed and/or suicidal between enrollment and completion of the study. Given a conservative estimate of a 20% screen failures and 20% dropout rate, we will need to recruit ~ 225 subjects to reach the target of 80 subjects for analysis. Psychiatric staff is available throughout each subject's participation, and can provide on-site emergency care in the event of crisis.

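### Objective 1 compares high and low CRP on raw post-minus-pre changes, and no Objective 1 model is stated to contain both CRP and pre-dose connectivity

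*Combined protocol and SAP*

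**What the plan says.** The design is a two-visit crossover with a resting-state scan before and after dosing at each visit, so each patient contributes four connectivity scores. Section 7, Analytic Strategy, Objective 1, plans three analyses of them:

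1. Linear models of post-dose Z scores, controlling for pre-dose Z scores and relevant covariates. CRP is not named.
2. Change scores: "The difference (delta; post minus pre) in connectivity Z scores before and after placebo and L-DOPA will also be compared by paired T test". The same sentence extends the comparison of these changes to two CRP groups, split at 3 mg/L.
3. A GLMM asking whether L-DOPA improves connectivity and whether the effect depends on CRP concentration. The covariates named are clinical and demographic; pre-dose connectivity is not among them.

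The section does not say which of the three is primary. The Objective 2 strategy, introduced as similar, does put CRP and the pre-dose score in the same linear model.

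The Power Analysis paragraph says "we will analyze an equal number of participants from low to high inflammation levels", about 27 in each of three CRP strata. Its effect size, "Based on our preliminary data, we anticipate large effect sizes (Cohen's dz" of about 1), is "for L-DOPA-induced increases in connectivity in patients with high inflammation". No effect size or power is given for high versus low CRP. For testing in general, "Statistics will be two-tailed with alpha <0.05".

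**The concern.** The Analysis Plan sets out to learn whether L-DOPA increases connectivity in patients with high versus low inflammation. That is a difference between two groups in a within-patient drug effect, with about 27 patients on one side and 53 or 54 on the other. Subtracting the pre-dose score from a 9-minute resting scan carries all of that score's noise into the outcome. Regressing on it removes only the part that predicts the post-dose score, and is never less precise apart from one degree of freedom.

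The other two analyses do not clearly recover this precision, because neither is said to hold CRP and pre-dose connectivity together. What is at stake is the precision of the moderation result. Type I error is not affected.

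**Working it through.** **The plan's own figure.** Paired t test, dz = 1, two-sided 0.05: power is 99.96% at n = 30 and 99.9% at n = 27. The stated figure of more than 80% holds as an inequality; n = 10 would already give 80.3%. This concerns the drug effect within high-CRP patients only.

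**Variance of the two contrasts.** Assume equal scan variance s², correlation w between the two scans of one visit, and correlation b between scans from different visits.

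- Raw change: D = (post-L-DOPA − pre-L-DOPA) − (post-placebo − pre-placebo), with Var(D) = 4s²(1 − w).
- Adjusted: regress (post-L-DOPA − post-placebo) on (pre-L-DOPA − pre-placebo). Each difference has variance 2s²(1 − b), and their correlation is r = (w − b)/(1 − b). The residual variance is 2s²(1 − b)(1 − r²).
- Ratio, raw over adjusted: 2/(1 + r).

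This gives 2.00 at r = 0, 1.54 at 0.3, 1.33 at 0.5, 1.11 at 0.8 and 1.00 at 1.

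**Power for high versus low CRP.** Both the correlations and the group difference of 0.6s are assumptions. Simulation with 27 v 53 patients, 6,000 trials per setting:

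| w / b | r | variance ratio | d on raw-change scale | power, raw change | power, adjusted |
|---|---|---|---|---|---|
| 0.5 / 0.4 | 0.17 | 1.71 | 0.42 | 42% | 63% |
| 0.6 / 0.4 | 0.33 | 1.50 | 0.47 | 51% | 67% |
| 0.7 / 0.4 | 0.50 | 1.33 | 0.55 | 63% | 74% |
| 0.8 / 0.5 | 0.60 | 1.25 | 0.67 | 80% | 88% |

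First row in full: Var(D) = 4(0.5) = 2.00s², so d = 0.6/√2.00 = 0.42. The adjusted variance is 2(0.6)(1 − 0.167²) = 1.167s², so d = 0.6/√1.167 = 0.56. Noncentral-t calculation agrees with the simulated powers to within about one percentage point.

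**Other effect sizes (27 v 54).** At d = 0.5 on the raw-change scale, power of 55% becomes 60% (r = 0.8), 68% (r = 0.5) or 84% (r = 0). At d = 1 it is already 98.7% and rises to at least 99.3%. The raw-change contrast reaches 80% power at d = 0.67.

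**What the GLMM would deliver.** If it takes all four scans with a drug × time × CRP term, then with complete data that term is the raw-change contrast and has its variance. If it takes post-dose scores only, without the pre-dose score, its variance exceeds the adjusted one by 1/(1 − r²): 1.03 at r = 0.17 and 1.56 at r = 0.6.

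**Which baseline to adjust for.** CRP groups are not randomised, and the Introduction reports lower connectivity with higher CRP. Take a single visit's change, an assumed 0.6 SD pre-dose gap (high CRP lower), w = 0.5 and equal true change in both groups. Adjusting for that visit's pre-dose score gives a group term of −0.6 + 0.5(0.6) = −0.30 SD. In simulation it was rejected about 29% of the time, against about 5% for the raw change. With the between-visit pre-dose difference the stable gap cancels, and rejection stayed at about 5%.

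**The case against.** **The plan already adjusts for the pre-dose scan.** It does so in the sentence before the change-score tests, which are introduced as an addition. A reader might infer that the plan subtracts the pre-dose score instead of ever adjusting for it. The documents do not support that. What remains is narrower: the adjusted model is not said to contain CRP.

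**The GLMM carries the CRP question.** This stands, so it would also be too strong to say that the CRP question rests on the change-score comparison alone. But the GLMM's named covariates omit pre-dose connectivity. The Objective 2 wording suggests the omission in Objective 1 may be one of drafting, but it does not fill the gap.

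**No power is lost at the plan's effect size.** True for the paired test in high-CRP patients. For the group contrast it is true only if d is near 1, for example if the effect is confined to high-CRP patients and the change scores vary equally in both groups. The plan gives no effect for low-CRP patients, so smaller contrasts cannot be excluded.

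**Twofold is a limiting case.** Correct. It needs a same-day pre-dose scan to predict no better than a scan from the other visit. At r = 0.8 the excess variance is 11%.

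**Change scores protect against baseline differences between non-randomised groups.** This is a sound reason to avoid single-visit adjustment. It does not count against adjusting for the between-visit difference.

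**This is a pilot with targeted and exploratory analyses.** That limits the weight of the point but does not remove it, since the change costs almost nothing.

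**Conclusion.** The point holds in limited form. No Objective 1 model is stated to include both CRP and pre-dose connectivity, and the one explicit high-versus-low comparison uses raw changes. Its variance is 1.11 to 2.0 times that of the adjusted contrast for r from 0.8 down to 0. In the four settings examined, with an assumed 0.6 SD difference, that corresponds to a power gain of about 8 to 21 percentage points.

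These sizes rest on assumed correlations, an assumed effect and equal scan variances; the documents supply none of them. The gain is small near d = 1, and none that matters applies to the paired test in high-CRP patients at dz of about 1. Validity is not in question, and expressing the sample size in dz is not a fault.

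**What to change.** For the L-DOPA-by-CRP contrast, regress each patient's (post-L-DOPA − post-placebo) on (pre-L-DOPA − pre-placebo) plus CRP, entered as log CRP or as >3 v <3 mg/L. The CRP coefficient is the moderation test. Alternatively, put equivalent pre-dose terms in the GLMM and state them: with post-dose scores as the outcome, each visit's pre-dose score together with the patient's mean pre-dose score.

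Name this as the primary moderation analysis and label the change-score t tests supportive. State that the baseline term is the between-visit pre-dose difference, and that a single visit's pre-dose score will not be used to adjust a comparison of CRP groups.

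The cost is SAP wording and one degree of freedom. No new data are needed, because all four scans are already planned.
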